7.3 Statistical Analysis Plan.....	21
8. REGULATORY CONSIDERATIONS.....	21
8.1 Participant Consent.....	22
8.2 Ethical Review.....	22
8.3 Sponsor.....	22
9. STUDY ADMINISTRATION.....	22
9.1 Protocol Deviations.....	22
9.2 Monitoring and Auditing.....	23
9.3 Study Documentation and Records Retention.....	23
9.4 Publication and Use of Study Findings.....	24
10. APPENDICES.....	25
11. REFERENCES.....	33

ABBREVIATIONS

AE	Adverse event
CI	Confidence interval
CPAP	Continue positive airway pressure
CRF	Case report form
CRS	Clinical respiratory score
ED	Emergency department
EUMF	Ege University Medical Faculty
FiO ₂	Fraction of inspired oxygen
FLUA	Influenza A
HR	Heart rate
HREC	Human Research Ethics Committee
HFNCOT	High-flow nasal cannula oxygen treatment
HRV	Human rhinovirus
IMV	Invasive mechanical ventilation
IND	Investigational new drug
IPPV	Intermittent positive pressure ventilation
LOS	Length of hospital stay
LOOT	Length of oxygen treatment
MD	Mean difference
NICE	National Institute for Health and Clinical Excellence
mPCR	Multiplex polymerase chain reaction
PEEP	Positive end-expiratory pressure
PEWS	Pediatric early warning score
ICU	Intensive care unit
PPU	Pediatric Pulmonology Unit
RCT	Randomised controlled study
RR	Respiratory rate
RSV A/B	Respiratory syncytial virus
SO ₂	Peripheral oxygen saturation
SOT	Standard oxygen treatment
St-FMOT	Standard face mask oxygen treatment
USA	United States of America
VBG	Venous blood gases

DEFINITIONS

Children

- ✓ In this study, is a child under the age of 24 months

Moderate and Severe bronchiolitis

- ✓ Defined as per CRS reported by Liu and colleagues (Appendices 1)
- ✓ Mild bronchiolitis: 0-4 point
- ✓ Moderate bronchiolitis: 5-8 point
- ✓ Severe bronchiolitis: 9-12 points

Supplemental Oxygen Requirement

- ✓ Peripheral capillary oxygen saturation (SpO_2) $<92\%$ while breathing room air

Standard Face Mask Oxygen Treatment (St-FMOT)

- ✓ The gas flow between 6.0 and 10.0 L/min

Rescue Treatment for St-FMOT

- ✓ First-tier, HFNCOT (2 L*kg/min) in the general ward
- ✓ Second-tier, admission to ICU for IMV

High-Flow Nasal Cannula Oxygen Treatment (HFNCOT)

- ✓ The gas flow at 2 L*kg/min or maximum 25 L/min

Rescue Treatment for HFNCOT

- ✓ Admission to ICU for IMV

STUDY SYNOPSIS

Title Comparison of high-flow nasal cannula and standard face mask oxygen therapy in children with moderate and severe bronchiolitis: A randomized controlled trial.

Trial Registry NCT04245202

Study Objectives

A. Primary Objectives

- ✓ To evaluate the effect on HR, RR, and CRS
- 1. The time it takes for HR to reach its normal range for age (hour)
- 2. The time it takes for RR to reach its normal range for age (hour)
- 3. The time it takes for CRS to regress from severe [scores of 9-12] to moderate [scores of 5-8] bronchiolitis, or from moderate [scores of 5-8] to mild [scores of 0-4] bronchiolitis (hour)

B. Secondary Objectives

- ✓ The decrease in HR compared with the baseline value
- ✓ The decrease in RR compared with the baseline value
- ✓ The decrease in CRS compared with the baseline score
- ✓ The effect on LOS and LOOT

C. Safety Objectives

- 1. The proportion of treatment failure at 4 hours or escalation of care
- 2. The proportion of admission to ICU for IMV
- 3. The proportion of adverse event

Rationale

- ✓ There has been insufficient RCT conducted on children with moderate and severe bronchiolitis requiring oxygen therapy in the general ward.

Study Population

A. Inclusion Criteria

- ✓ Children aged between 1 and 24 months with moderate and severe bronchiolitis requiring oxygen supplement.

B. Exclusion Criteria

- ✓ Children with mild bronchiolitis
- ✓ Those with not requiring oxygen therapy
- ✓ Those admitted to ICU for urgent IMV
- ✓ Those who received supplemental oxygen or HFNCOT at other facilities before arrival

- ✓ Those with known comorbidity (such as congenital heart disease, chronic lung disease, neuromuscular disease, metabolic disease, and immunocompromised)
- ✓ Those with a craniofacial malformation, an upper airway obstruction, pneumothorax, or nasal trauma

Study Design

- ✓ Open-label, two-arm, phase 4 randomized controlled trial

Sample size (each group)

- ✓ 55 in each group (HFNCOT and St-FMOT)

Investigational treatment:

- ✓ Fisher & Paykel MR850 with Optiflow™ Junior Nasal Cannula System

Control Group

- ✓ St-FMOT

Duration of Treatment

- ✓ From admission to EUMF Pediatric Hospital to at 15 days of post-discharge

Centre/s

- ✓ Single-center – EUMF/Pediatric Hospital

Statistical Methods

- ✓ Chi-Squared Test, Fisher's Exact Test, Mann-Whitney-U Test, Linear Mixed Model, Bruner Langer Method

SCHEDULE OF OBSERVATIONS AND PROCEDURES

Diagnosis bronchiolitis	Screening ED or PPU	1h	2h	4h	12h	24h	48h	72h	96h	Phone follow-up
Inclusion/Exclusion criteria	X									X**
Informed consent	X									
Medical History	X									
Physical exam	X	X	X	X	X	X	X	X	X	
Bodyweight and length	X									
Body temperature (°C)	X	X	X	X	X	X	X	X	X	
Heart rate (beat per min)†	X	X	X	X	X	X	X	X	X	
Respiratory rate (breath per min)†	X	X	X	X	X	X	X	X	X	
Arterial blood pressure (mmHg)†	X	X	X	X	X	X	X	X	X	
Clinical respiratory score†	X	X	X	X	X	X	X	X	X	
PCR	X									
Blood sample*	X									
VBG*	X			X						
Concomitant Medications	X	X	X	X	X	X	X	X	X	
Medical treatment‡	X	X	X	X	X	X	X	X	X	
Adverse event record	X	X	X	X	X	X	X	X	X	

If the patient was not discharged after 96 hours, the procedures mentioned above were continued.

†All parameters were measured during the resting of children.

*Samples were performed at any time if the clinician deemed it necessary.

Protocol No 1
Date: 10/03/2017
Revised 1: 10/03/2020
Revised 2:14/02/2021

**All children included in the study were phoned after 15 days post-discharge.

†The clinician decides to use medical treatments such as beta2 agonist, systemic steroid, and hypertonic saline.

1. INTRODUCTION

1.1 Background

Acute bronchiolitis is globally one of the most considerable health burdens for children. It is estimated that approximately 34 million children under five years suffer from lower respiratory tract infection, with 3.4 million admissions to hospital and about 199,000 deaths per year, especially in developing countries.¹ In the seminar conducted by Florin and colleagues,² they reported that the role of medical therapies in children with bronchiolitis was investigated many times. Still, none of these treatments has shown efficacy. The NICE and AAP guidelines³ recommend supportive therapies, including oxygen supplementation, respiratory support, and hydration. There are currently three ways of delivering oxygen to pediatric patients;

- ✓ Invasive mechanical ventilation, e.g., IPPV in critical care settings, or
- ✓ Non-invasive ventilation, e.g., CPAP predominantly in critical care settings, or
- ✓ Via nasal cannulae, mask, or head-box in ward settings.

High-flow nasal cannula oxygen treatment (HFNCOT) has become an increasingly widespread practice for managing bronchiolitis in recent years. Still, it is not recommended for treating bronchiolitis, according to the current NICE guidelines.³ Although HFNCOT has been performed extensively for many years in the neonatal population, support for its safety and efficacy in children is still somewhat limited.⁴ Previous observational and physiological studies suggested that HFNCOT may decrease respiratory effort, reduce intubation rates, and improve gas exchange.^{5,6} Conversely, other reports showed that HFNCOT results in no significant changes in the RR, LOS, and the quality of ICU admission for IMV.⁷⁻⁹ Although these reports represent an excellent progression in the daily clinical management of bronchiolitis and contribute valuable information to the literature, the major problem in this area is the lack of an adequate number of RCTs.

1.2 High-Flow Nasal Cannula Oxygen Delivery

Warmed humidified titrated medical air/oxygen is delivered through a non-sealing nasal cannula. The Optiflow™ system manufactured by Fisher & Paykel allows humidified flows of up to 25 L/min to be given. There is wide variation in the flows used and methods used to calculate them; however, flows are more remarkable than the standard maximum of 2 L/min. Those who exceed the patient's tidal volume are usually described as high flow. The effective delivery of high-flow oxygen at optimal humidity with dead space flushing and an element of positive airway pressure is expected to be beneficial in managing acute bronchiolitis.⁵ Previously published studies showed that HFNCOT notably decreases in HR and RR relative to St-FMOT.¹⁰⁻¹² In contrast, it was illustrated that children

treated with HFNCOT had identical results in reducing the HR and RR compared with those treated with St-FMOT.^{4,13} Otherwise, there are conflicting results in the literature regarding whether HFNCOT decreases CRS compared with SOT. Some prospective trials^{14,15} did not show a considerable reduction when comparing between HFNCOT and SOT.

In contrast, others showed that HFNCOT is more effective in reducing CRS than SOT.^{16,17} High-flow oxygen has been found to lower intubation rates and decrease the LOS for children in ICU settings.^{6,13} The Schibler et al.⁶ study followed the introduction of high-flow oxygen for bronchiolitis and found intubation rates dropped from 37% to 7% over four years as usage increased from use in 13% of patients to 66% by 2009. This RCT aims to address the gap in knowledge by studying the Fisher & Paykel® humidification system with Optiflow nasal prongs used in the care of children aged between 1 and 24 months with moderate and severe bronchiolitis requiring oxygen supplementation. Bronchiolitis was selected as there is a significant disease burden in this age group due to a variety of viral causative organisms, and no other effective medical treatment may confound results.

1.3 Study Design Rationale

This study includes a single site longitudinal observational cohort study [HREC (03.14.2017/No: 17-2.1/18)] nested within an open, two-arm randomized control trial HFNCOT compared to St-FMOT in the management of moderate and severe bronchiolitis requiring oxygen supplementation in children aged between 1 and 24 months.

2. STUDY OBJECTIVE

2.1 Study Question

In children aged between 1 and 24 months with moderate and severe bronchiolitis requiring oxygen supplementation, does HFNCOT delivered via a Fisher & Paykel MR850 humidifier with Optiflow Junior prongs compared to St-FMOT decrease HR, RR, and CRS during the acute admission?

2.2 Primary Objectives

- ✓ The median time it takes for HR to reach its normal range for age (hour)
- ✓ The median time it takes for RR to reach its normal range for age (hour)
- ✓ The median time it takes for CRS to regress from severe [scores of 9-12] to moderate [scores of 5-8] bronchiolitis, or from moderate [scores of 5-8] to mild [scores of 0-4] bronchiolitis (hour)

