7.2 Data Analysis Methods

Categorical and continuous variables will be expressed as frequency (percentage) and median (IQR). Between groups, we will use the Mann-Whitney-U test for comparing the time of success for HR, RR, and CRS (SPSS Inc., version 25.0, Chicago, IL, USA). The longitudinal analysis part of the study will be performed non-parametrically with the Brunner Langer model for CRS conducted with a linear mixed model in a parametric way for HR and RR. Brunner Langer model (F1-LD-F1) is applied using web-based software (R software, version 3.5.2, package: nparLD, R Foundation for Statistical Computing, Vienna, Austria; <http://r-project.org>). The PROC MIXED procedure in the SAS software is used (Version 9.3; SAS Institute, Cary, NC, USA) to perform linear mixed models in which subjects will be included as random effects. When there is a significant interaction effect in the longitudinal analysis ($P < .1$), the time effect will be analyzed in each group, and groups will be compared at baseline and following time points (the baseline was subtracted from these time points). The proportions of the treatment failure at 4 hours, rescued patient, ICU admission, and AE are analyzed using Fisher's Exact test and given with odds ratio (OR) and 95% Confidence Interval (CI). We will perform intention-to-treat and per-protocol approaches for all outcomes. The time of success for HR, RR, and CRS outcomes will be analyzed using the PP approach. A 2-sided $P < .05$ defines statistical significance.

Statistical Analysis Plan

The biostatistician in the study, which has blinded to allocation, will perform the analysis. An interim analysis will not be performed. If substantial evidence of increased risk of harms ($p < 0.001$) observed in both groups, stopping rules will be used with the biostatistician's advice. Intention to treat and per-protocol approaches will be conducted if necessary.

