Respiratory rate (breaths/minute)	0 to < 3 months	> 29 and < 61	≥ 61 or ≤ 29	≥ 81 or ≤ 19	≥ 91 or ≤ 15
	3 to < 12 months	> 24 and < 51	≥ 51 or ≤ 24	≥ 71 or ≤ 19	≥ 81 or ≤ 15
	1-4 years	> 19 and < 41	≥ 41 or ≤ 19	≥ 61 or ≤ 15	≥ 71 or ≤ 12
	>4-12 years	> 19 and < 31	≥ 31 or ≤ 19	≥ 41 or ≤ 14	≥ 51 or ≤ 10
	>12 years	> 11 and < 17	≥ 17 or ≤ 11	≥ 23 or ≤ 10	≥ 30 or ≤ 9
Respiratory effort		Normal	Mild increase	Moderate increase	Severe increase/any apnea
Oxygen saturation (%)		> 94	91 to 94	≤ 90	

Protocol No 1
Date: 10/03/2017
Revised 1: 10/03/2020
Revised 2:14/02/2021

Oxygen therapy		Room air		Any to < 4 L/minute or < 50%	≥ 4 L/minute or $\geq 50\%$
-----------------------	--	----------	--	------------------------------	----------------------------------

Appendices 4. Case report form

Case No and date								
Age (months)								
Gender	 Male		 Female					
Gestational age								
Body weight (gr/kg)								
Virus detected in RT-PCR	 Yes		 No					
If yes, which virus was detected								
Number of bronchiolitis	 1		 2		 3+			
Season	 Winter		 Autumn		 Spring		 Summer	
Study device	 St-FMOT  HFNCOT							
VARIABLES	Body temperature (°C)	Heart rate (bpm)	Respiratory rate (/min)	Arterial tension (mm/Hg)	SpO ₂ (%)	Venous blood gases	Ph-PCO ₂	CRS
At first admission								
1 h								
2 h								
4 h								
12 h								
24 h								

2 d							
3 d							
4 d							
5 d							
6 d							
7 d							
8 d							
9 d							
10 d							
Length of oxygen requirement (h)							
Length of hospital stay (d)							
Beta2 mimetic use?	 Yes		 No				
If yes, how many days did it use? (d)							
Inhaler corticosteroid use?	 Yes		 No				
If yes, how many days did it use? (d)							
IV corticosteroid use?	 Yes		 No				
If yes, how many days did it use? (d)							
Inhaler hypertonic saline use?	 Yes		 No				
If yes, how many days did it use? (d)							
Did any complications occur?	 Yes		 No				

Which complications occurred?			

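### The three primary recovery times are known only to lie between visits up to 24 h apart, so the arm medians in hours can hide or inflate a difference; add an interval-censored estimate beside the Mann-Whitney test

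*Combined protocol and SAP*

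**What the plan says.** Section 2.2 states the first two primary objectives as "The median time it takes for HR to reach its normal range for age (hour") and "The median time it takes for RR to reach its normal range for age (hour"). The third is the median time in hours for CRS to drop one severity class.

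The Schedule of Observations and Procedures has columns after screening at "1h 2h 4h 12h 24h 48h 72h 96h", with HR, RR and "Clinical respiratory score" marked in each. A footnote extends observation: "If the patient was not discharged after 96 hours, the procedures mentioned above were continued". The case report form in Appendices 4 has rows at 1, 2, 4, 12 and 24 h and then daily from 2 d to 10 d. It has a duration field for "Length of oxygen requirement (h"), and others for hospital stay and drug use. It has none for the hour at which HR, RR or CRS reached target.

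Section 7.2 gives the summary, "Categorical and continuous variables will be expressed as frequency (percentage) and median (IQR"), and the test: "Between groups, we will use the Mann-Whitney-U test for comparing the time of success for HR, RR, and CRS". It does not say how the hour of recovery is derived, names no method for times known only to lie between visits, and gives no effect measure or confidence interval for the primary times. Odds ratios with 95% CI are specified only for the proportions.

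**The concern.** If a child is off target at one visit and on target at the next, recovery happened somewhere between the two. The gaps are 1, 1 and 2 h up to 4 h, then 8 h, 12 h and 24 h thereafter. A time in hours taken from these records is really an interval, and beyond 4 h the interval is wide compared with the differences a bronchiolitis trial might hope to show.

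With no effect measure specified, readers will judge the size of benefit by comparing the two arm medians. Each can fall essentially only on a visit time or, with an even number of children, halfway between two. The apparent benefit therefore moves in steps of about 8, 12 or 24 h once medians pass 4 h. A real difference inside one gap disappears, and a small one that straddles a visit is enlarged. All three primary outcomes are affected.

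**Working it through.** **Inputs from the documents.** Visit times as above (Schedule; Appendices 4). Power 80%, alpha 0.05, 1:1 allocation, totals of 100 (CRS), 38 (RR) and 43 (HR), 10% attrition, final total 110 (sections 3.1 and 7.1). Two-sided testing (section 7.2).

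**The plan's own figure.** 100 × 1.10 = 110, as stated. Dividing instead, 100 / 0.90 = 111.1, rounded up to 112. The point does not depend on which is used. The totals of 100, 38 and 43 cannot be rebuilt because no effect or SD is given.

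**Step 1: direct arithmetic, no distribution needed.** Assign each recovery to the first visit at target:

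| True medians (h) | True difference (h) | Read from visits (h) | Visit difference (h) |
|---|---|---|---|
| 5 v 11.5 | 6.5 | 12 v 12 | 0 |
| 13 v 23 | 10 | 24 v 24 | 0 |
| 25 v 47 | 22 | 48 v 48 | 0 |
| 11 v 13 | 2 | 12 v 24 | 12 |
| 23 v 25 | 2 | 24 v 48 | 24 |

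**Step 2: effect sizes implied by the stated totals.** The normal approximation is d = (1.960 + 0.842) × √(4/N). For N = 100 this is 2.802 × 0.200 = 0.560. The exact t-test solution is 0.566 for CRS, 0.875 for HR (N = 43) and 0.934 for RR (N = 38).

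**Step 3: how often the medians mislead.** These assumptions are not in the documents: log-normal times, SD of log time (σ) 0.6 to 1.2, control median 4 to 72 h, 50 children per arm, and an arm effect of d on the log scale. The true ratio of medians is exp(−d × σ); for CRS with σ = 0.8 it is exp(−0.566 × 0.8) = 0.636. Each time is moved up to the next visit. Error is the root mean square error (RMSE) of the difference in medians, divided by the true difference and averaged over control medians.

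| d | σ | Visit medians equal: average (range) | RMSE, exact times | RMSE, visit times |
|---|---|---|---|---|
| 0.566 (CRS) | 0.6 | 51% (7–100%) | 0.45 | 1.62 |
| 0.566 | 0.8 | 38% (5–97%) | 0.46 | 1.36 |
| 0.566 | 1.2 | 21% (4–66%) | 0.49 | 1.10 |
| 0.875 (HR) | 0.6 | 31% (1–98%) | 0.30 | 1.19 |
| 0.875 | 1.2 | 5% (1–27%) | 0.35 | 0.85 |
| 0.934 (RR) | 0.6 | 27% (0–99%) | 0.28 | 1.13 |
| 0.934 | 1.2 | 4% (0–17%) | 0.34 | 0.83 |

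In these rows the visit schedule multiplies the error by 2.2 (1.10 / 0.49) to 4.0 (1.13 / 0.28).

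**Step 4: dependence on location.** With σ = 0.8, the CRS-sized effect and 49 per arm (110 × 0.9 / 2 = 49.5, rounded down), the visit medians are equal in about 95% of trials when the true medians are 8.0 v 5.1 h, both inside the 4–12 h gap. At 18 v 11.4 h (true difference 6.6 h) they are equal in about 37% and 12 h apart in about 60%. At control medians of 5, 14 and 30 h they are equal in about 11%, 15% and 11%.

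**Step 5: the rank test.** For the CRS-sized effect and control medians of 4 to 60 h, Mann-Whitney power is about 77–80% with exact times and 69–79% with visit times, a loss of about 0 to 9 points. A further set of log-normal runs put the largest loss at about 12. For HR and RR the loss is about 0 to 2 points. With normal rather than log-normal times, the CRS-sized loss ranged from 2 to 21 points, the larger values needing tightly clustered recovery times.

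**The case against.** Several points on the other side stand.

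- The plan does not name a difference in median hours as its effect measure. It gives medians by arm and a rank test. The problem arises when those medians are compared, which the plan invites by offering nothing else.
- Reading times from the visits is an inference. Section 5.1 describes hourly checks of oxygen need on the face mask and section 5.2 hourly steps in flow, so staff see children between visits. But the case report form has nowhere to record HR, RR or CRS from those contacts. If hours come from another source, the plan needs to say so, particularly in an open-label trial.
- Observation does not stop at 96 h. It continues, with daily rows to 10 d; the 24 h spacing remains.
- The secondary longitudinal analyses use the visit values directly and need no recovery time. They do not supply an estimate for the primary outcomes.

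Two stronger readings are tempting. A reader might infer that the reported difference mostly reflects the schedule. The documents do not support this as a general statement: it depends on recovery-time distributions they do not give, the 95% result is close to a worst case, and with wide spreads and HR- or RR-sized effects equal medians are uncommon. A reader might also infer that the primary p-values are unsound. They are not on this ground: the rank test accommodates ties and, with log-normal times, loses little power.

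**Conclusion.** The concern holds as a defect in how the primary effects will be estimated and reported. On the schedule and case report form as written, the three primary times are interval-censored, no derivation rule is given, and the arm medians can be equal when recovery differs or far apart when it hardly differs. That possibility follows from the visit times alone.

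Its frequency rests on the assumed log-normal distributions. For a CRS-sized effect, equal medians occur in 21% to 51% of trials on average; for HR- and RR-sized effects the averages run from 4% to 31%. In every combination tabulated, error from the schedule exceeds the sampling error that exact times would leave. The significance test is only modestly affected. This is an inexpensive improvement worth making, not a flaw that invalidates the primary comparison.

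**What to change.** In section 7.2:

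1. Define each primary time as lying between the last visit not at target and the first visit at target, with an open upper end for a child not yet at target when last seen. If another source of the hour is intended, name it.
2. Keep the Mann-Whitney test, applied to the order of visits.
3. For each of HR, RR and CRS, add an arm effect with 95% CI from an interval-censored model (time ratio) or a grouped-time model (hazard ratio), and state the model in advance.
4. Label any reported median as a visit time.
5. If wanted, show the proportions at target by 4, 12 and 24 h descriptively. Testing them would add nine comparisons (three outcomes at three times) for which the plan has no multiplicity rule.

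The primary objectives can stay as they are, and no visits or data items are added. The cost is a paragraph of text and a little more analysis. The downside is a ratio that is less familiar than hours and rests on a modelling assumption. In simulation, a log-normal interval-censored fit returned time ratios of 0.64 to 0.65 against a true 0.636, but the data were generated from the same model. This shows only that the visit data suffice when the model is right, so a second model form is a sensible sensitivity check.

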2.3 Secondary Objectives

- ✓ The mean difference in HR decreased compared with the baseline value from randomization to 96 hours (or to discharge)
- ✓ The mean difference in RR decreased compared with the baseline value from randomization to 96 hours (or to discharge)
- ✓ The mean difference in CRS regress compared with the baseline value from randomization to 96 hours (or to discharge)
- ✓ The length of hospital stays [from admission to discharge (hour)]
- ✓ The length of oxygen treatment [from admission to weaning to room air (hour)]

